9.4.5 Safety Analyses

Safety analysis will be primarily MITT where individuals who receive assignment but do not receive any product are excluded. Because of blinding and the brief length of time between assignment and administration, such cases will be very few.

Safety data will be presented by line listing and tables at the individual level to provide details on safety events such as severity, duration, and relationship to study product. The number and percentage of subjects with 1 or more AEs will be summarized by dose arm along with the exact 95% confidence intervals of the AE rate. For subjects experiencing more than 1 AE, the subjects will be counted once under the event of highest severity.

In the efficacy study, comparisons between the dose arms and the control arm will be additionally performed in terms of the proportions of solicited AEs, related AEs, and SAEs.

In the rare case of subjects receiving a regimen different from assignment, a per-protocol analysis will be performed as a secondary analysis, which will include subjects according to the product they actually receive in the study.

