3 OBJECTIVES AND ENDPOINTS

OBJECTIVES	ENDPOINTS	JUSTIFICATION FOR ENDPOINTS
Primary		
1. Dose escalation: To evaluate the safety and tolerability of CIS43LS administered IV at 5,	1. Dose escalation: Incidence and severity of local and systemic AEs occurring within 7 days after the administration of CIS43LS.	1. Assessment of AEs is a standard measure of study

Abbreviated Title: Anti-malaria MAb in Mali

Version Date: October 13, 2022

OBJECTIVES	ENDPOINTS	JUSTIFICATION FOR ENDPOINTS
10, and 40 mg/kg in healthy Malian adults. 2. Efficacy: To determine if IV administration of CIS43LS at 10 mg/kg and 40 mg/kg (compared to placebo) mediates protection against naturally occurring Pf infection in healthy Malian adults during a single malaria season as detected from microscopic examination of thick blood smear.	2. Efficacy: Pf blood stage infection as detected by microscopic examination of thick blood smear for 24 weeks after administration of CIS43LS or placebo.	agent safety and tolerability. 2. Blood smear is the gold standard for diagnosis of blood-stage Pf infection.
Secondary		
1. Dose escalation: To evaluate the PK of CIS43LS at each dose level throughout the study. 2. Efficacy: To determine if IV administration of CIS43LS at 10 mg/kg and 40 mg/kg (compared to placebo) mediates protection against naturally occurring Pf infection in healthy Malian adults during a single malaria season as detected by RT-PCR. 3. Efficacy: To evaluate the PK of CIS43LS throughout the study at the dose of 10 mg/kg and 40 mg/kg and to correlate CIS43LS serum concentration with Pf infection risk.	1. Dose escalation: Measurement of CIS43LS in sera of recipients. 2. Efficacy: Pf blood stage infection as detected by RT-PCR for 24 weeks after administration of CIS43LS or placebo. 3. Efficacy: Measurement of CIS43LS in sera of recipients.	1. Concentrations of CIS43LS in blood will help assess durability of CIS43LS at each dose level. 2. RT-PCR is more sensitive than blood smear for detecting Pf blood-stage infection. 3. Concentrations of CIS43LS in blood will help assess durability of CIS43LS and will allow for correlation with Pf infection risk.
Tertiary/Exploratory		

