8.4 SAFETY DEFINITIONS, MANAGEMENT, AND SPONSOR REPORTING

8.4.1 Definitions

Adverse Event: An AE is any untoward or unfavorable medical occurrence in a human subject, including any abnormal sign (e.g., abnormal physical exam or laboratory finding), symptom, or disease, temporally associated with the subject's participation in the research, whether or not considered related to the research.

Adverse Reaction: An AR means any AE caused (see "Causality" below) by a study agent. ARs are a subset of all suspected adverse reactions (SARs; defined below) where there is reason to conclude that the study agent caused the event.

Suspected Adverse Reaction: SAR means any AE for which there is a reasonable possibility that the study agent caused the AE.

Per US FDA guidance:

For the purposes of IND safety reporting, "reasonable possibility" means there is evidence to suggest a causal (see "Causality" below) relationship between the study agent and the AE. A SAR implies a lesser degree of certainty about causality than an AR, which means any AE caused by a study agent.

SARs are the subset of all AEs for which there is a reasonable possibility that the study agent caused (see "Causality" below) the event. Inherent in this definition, and in the requirement to report SARs, is the need for the sponsor to evaluate the available evidence and make a judgment about the likelihood that the study agent actually caused the AE.

The sponsor is responsible for making the causality judgment.

Serious Adverse Event: An SAE:

- is an AE that results in death.

Abbreviated Title: Anti-malaria MAb in Mali

Version Date: October 13, 2022

- is an AE that is life-threatening event (places the subject at immediate risk of death from the event as it occurred).
- is an AE that requires inpatient hospitalization or prolongs an existing hospitalization.

NOTE:

- Hospitalization is considered required if outpatient treatment would generally be considered inappropriate.
- Same-day surgical procedures that are required to address an AE are considered hospitalizations, even if they do not involve an overnight admission.

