8.4.2 Documenting, Assessing, Recording, and Reporting Events

ALL AEs, including those that may appear to have a non-study cause (see “Causality” below), will be documented (e.g., on the clinical chart/progress notes/clinical laboratory record), recorded (e.g., in the study-specified CRF/research database), and reported (e.g., cumulatively from the research database, or according to protocol-specified expedited reporting mechanism) to the sponsor from the time informed consent is obtained through the timeframe specified below. At each contact with the subject, information regarding AEs will be elicited by open-ended questioning and examinations.

AEs and SAEs will generally be recorded, assessed, and reported according to the timeframes outlined in [Table 2](#).

Abbreviated Title: Anti-malaria MAb in Mali

Version Date: October 13, 2022

Table 2. Standard event recording, assessment, and reporting timeframes.

Event type	Record, assess, and report through
Related SAEs	End of subject participation in study, or if study personnel become aware thereafter
Unrelated SAEs	End of subject participation in study
Related non-serious AEs of grade 1 to 3	End of subject participation in study
All other related non-serious AEs	End of subject participation in study
Unrelated non-serious AEs	End of subject participation in study

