9 STATISTICAL CONSIDERATIONS

9.1 STATISTICAL HYPOTHESIS

The hypotheses are that CIS43LS will be safe and will confer protection against Pf infection. In the dose-escalation study, the primary objective is to evaluate the safety and tolerability. In the efficacy study, the primary objective is to evaluate the safety and efficacy of CIS43LS compared to placebo.

Primary Endpoints:

- Dose escalation: Incidence and severity of local and systemic AEs occurring within 7 days after the administration of CIS43LS
- Efficacy: Pf blood stage infection as detected by microscopic examination of thick blood smear for 24 weeks after administration of CIS43LS or placebo

Abbreviated Title: Anti-malaria MAb in Mali

Version Date: October 13, 2022

Secondary Endpoints:

- Dose escalation: Measurement of CIS43LS in sera of recipients
- Efficacy: Pf blood stage infection as detected by RT-PCR for 24 weeks after administration of CIS43LS or placebo
- Efficacy: Measurement of CIS43LS in sera of recipients

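### The efficacy study's any-AE, highest-severity and SAE summaries run through the malaria season without separating malaria, so protection by CIS43LS can dilute late or nonspecific harm in them

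*Combined protocol and SAP*

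**What the plan says.** Section 9.4.5 sets out the safety summary: "The number and percentage of subjects with 1 or more AEs will be summarized by dose arm along with the exact 95% confidence intervals". Its counting rule is: "For subjects experiencing more than 1 AE, the subjects will be counted once under the event of highest severity". For the efficacy study it then adds comparisons of each dose arm with control "in terms of the proportions of solicited AEs, related AEs, and SAEs". No time window is given for any of these, and malaria is not mentioned.

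What enters the tables is set in section 8.4. An AE includes "any abnormal sign (e.g., abnormal physical exam or laboratory finding), symptom, or disease". Section 8.4.2 has the study record "ALL AEs, including those that may appear to have a non-study cause", and Table 2 carries this to the end of participation even for unrelated non-serious events. Section 8.4.2.2 records a clinical diagnosis as the AE in place of its separate signs and symptoms. No section exempts malaria.

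The only AE endpoint with a window is the dose-escalation one in section 3: "Incidence and severity of local and systemic AEs occurring within 7 days after the administration of CIS43LS". For the randomized part, section 9.1 states: "In the efficacy study, the primary objective is to evaluate the safety and efficacy of CIS43LS compared to placebo". Efficacy follow-up lasts 24 weeks after infusion (section 1.1), and section 4.1 describes intense seasonal transmission from July through December.

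**The concern.** The same clinical events feed both the benefit and the harm tables. A symptomatic malaria episode is recorded as an AE under its diagnosis, and the trial expects fewer of these on CIS43LS. A lower any-AE or SAE proportion on CIS43LS may therefore reflect protection, and an equal proportion may conceal an excess of other events.

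The highest-severity rule adds to this. A subject with a mild early event and a more severe malaria episode later appears only in the more severe row. If the product works, this happens more often on placebo, so the severity distribution also tilts toward CIS43LS.

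At stake is the only placebo-controlled safety evidence in the protocol: 220 subjects assigned to CIS43LS and 110 to placebo. The exposed harms are those that the solicited and related categories would not catch: late events, nonspecific events, and events attributed to another cause.

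**Working it through.** **Inputs from the documents.** 110 per arm; Table 5 at a 5.0% placebo AE rate, two-sided alpha 0.025; Table 4 placebo infection 0.4 to 0.7 and protective efficacy (PE) 0.4 to 0.6.

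**Inputs assumed.** The share s of infections that become AEs (10%, 25%, 50%); malaria and other AEs independent; PE against malaria AEs equal to PE against infection.

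**Step 1: reproduce Table 5.** For two proportions p and q with mean p̄, n per arm and z = 2.241,

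power = Φ{ [ |q − p|√n − z√(2p̄(1 − p̄)) ] / √(p(1 − p) + q(1 − q)) }.

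With n = 110, p = 0.05 and q = 0.182, power is 79.8%. With q = 0.207 it is 89.9%. Table 5 lists these differences (13.2 and 15.7 points) at 80% and 90%. All 15 rows agree within 0.1 point, so Table 5 is not in error.

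**Step 2: add malaria.** Let b = 0.05 be the non-malaria AE rate, h = 0.132 the true harm, and m = placebo infection × s.

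- Placebo any-AE rate: 1 − (1 − b)(1 − m)
- CIS43LS any-AE rate: 1 − (1 − b − h)(1 − m(1 − PE))

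For example, infection 0.4 and s = 0.25 give m = 0.10. Placebo is 1 − 0.95 × 0.90 = 14.5%, and CIS43LS is 1 − 0.818 × 0.95 = 22.3%.

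| Placebo infection | s | m | Placebo | CIS43LS | Difference (points) | Power |
|---|---|---|---|---|---|---|
| malaria excluded | – | 0 | 5.0% | 18.2% | 13.2 | 79.8% |
| 0.4 | 10% | 0.04 | 8.8% | 19.8% | 11.0 | 53.8% |
| 0.4 | 25% | 0.10 | 14.5% | 22.3% | 7.8 | 22.5% |
| 0.4 | 50% | 0.20 | 24.0% | 26.4% | 2.4 | 3.3% |
| 0.7 | 10% | 0.07 | 11.7% | 21.1% | 9.4 | 36.1% |
| 0.7 | 25% | 0.175 | 21.6% | 25.4% | 3.7 | 5.6% |
| 0.7 | 50% | 0.35 | 38.3% | 32.5% | −5.7 | sign reversed |

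PE is 0.5 throughout. At infection 0.4 and s = 0.25, PE 0.4 gives 1 − 0.818 × 0.94 = 23.1% on CIS43LS (power 27%), and PE 0.6 gives 1 − 0.818 × 0.96 = 21.5% (power 18%).

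**Step 3: how much is due to protection.** With no protection the difference would be h(1 − m), because a subject with malaria is already counted. At infection 0.4 that is 12.7, 11.9 and 10.6 points for the three values of s. Protection removes a further (1 − b − h) × m × PE: 0.818 × 0.02 = 1.6, 0.818 × 0.05 = 4.1 and 0.818 × 0.10 = 8.2 points. The rest of the power loss comes from the higher base rate.

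**Step 4: SAEs.** Use the Table 5 row with a 1.0% placebo rate and a 9.7-point difference. Power is 80.0% with no malaria SAEs. If 1%, 2% or 5% of placebo subjects have a malaria SAE (assumed; the documents give no rate) and PE is 0.5, power is 69.4%, 58.7% or 31.8%.

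**Step 5: alpha.** Section 9.4.1 sets 0.05 where nothing else is specified. At 0.05 the contrasts at infection 0.4 are 86.9% with malaria excluded and 64.9%, 31.9% and 6.0% pooled. The pattern is the same.

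**The case against.** The strongest objection is that two of the three planned comparisons are largely shielded. Section 6.1.2.4 describes solicited symptoms as assessed before discharge on day 0 and followed until resolved. Section 8.4.2.1.2 leads an event with a proven alternative cause to be classed as unlikely or not related, under blinding and with sponsor review. This stands. A reader might infer that an excess of infusion reactions would be hidden; the documents do not support that, because it should appear in the solicited and related comparisons.

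The any-AE table is descriptive, and section 9.4.5 plans no test on it. This also stands, so the power figures for any-AE measure lost information and are not the operating characteristics of a planned test. SAEs are a planned comparison.

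A reader might also count every positive smear as a laboratory AE. No section says so. Smears are an efficacy evaluation (section 8.2.3), the safety laboratories are CBC, ALT and creatinine (section 8.3), and Appendix B has no smear row. Nor should Table 5's detectable differences be applied to much higher base rates, since its placebo rates stop at 5.0%.

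Sections 1.1 and 3 list only protection as the efficacy study's primary objective, while section 9.1 adds safety. The point does not depend on which reading prevails.

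Finally, line listings carry severity, duration and relationship, so malaria could be separated later. That is true, but nothing pre-specifies it, and a split chosen after unblinding carries less weight.

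**Conclusion.** The point holds for the any-AE summary, the highest-severity summary and the SAE comparison in the efficacy study. It does not extend to the safety analysis as a whole. Expected protection lowers these proportions on CIS43LS and can dilute harms that are late, nonspecific or not judged related.

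The direction follows from the plan's own expectation of efficacy. The size does not, because neither the share of infections that become AEs nor the malaria SAE rate is given. At 40% placebo infection and 50% efficacy, a contrast with about 80% power falls to about 54% if one infection in ten becomes an AE and to about 3% if half do. The sign reverses only in the heaviest setting examined: 70% infection with half becoming AEs. No stated figure in the plan is wrong. This is a cheap improvement to the safety reporting.

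**What to change.** In section 9.4.5, for the efficacy study, keep the all-AE table and pre-specify beside it:

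1. By-arm any-AE, severity and SAE summaries that exclude malaria events, with exact 95% confidence intervals as already planned.
2. The highest-severity count applied after that exclusion.
3. Malaria events on their own line, by arm.
4. A rule, fixed before unblinding and applied blind, for what counts as a malaria event and where its complications are placed. It should also say whether an asymptomatic positive smear is recorded as an AE.

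A descriptive table for a fixed early post-infusion window may be added as support. It need not become the main safety comparison.

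The cost is SAP wording, extra tables from data already collected, and the attribution rule. Because that rule involves judgement, the all-inclusive figures should stay alongside.

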8.4.3.2 Replacement of Withdrawn Subjects or Subjects Who Discontinue Study Agent

In the dose-escalation study, subjects withdrawn prior to the day 7 safety evaluation will be replaced. In the efficacy study, subjects withdrawn prior to study agent administration will be replaced.

All subjects exposed to study agents MUST be included in the safety dataset.

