9.3 POPULATIONS FOR ANALYSES

The following datasets will be considered in study analyses:

- Intention-to-treat (ITT) analysis dataset will include all subjects that receive assignment and will be analyzed according to the initial randomization assignment.
- Modified intention-to-treat (MITT) analysis dataset will include all randomized subjects that receive the study intervention and will be analyzed according to the initial randomization assignment.
- Per-protocol analysis dataset will include all randomized subjects that receive the study intervention consistent with the initial randomization assignment and complete the scheduled visits, and will be analyzed according to the initial randomization assignment. In cases where subjects receive an intervention other than the one randomly assigned, an as-treated analysis will be additionally performed according to the actual intervention received.

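### The primary safety analysis groups subjects by the arm assigned rather than the product received, and section 9.4.5 gives the planned by-product analysis a name that section 9.3 defines differently.

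*Combined protocol and SAP*

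**What the plan says.** Section 9.4.5 names the primary safety population: "Safety analysis will be primarily MITT where individuals who receive assignment but do not receive any product are excluded". Section 9.3 says that the MITT set "will include all randomized subjects that receive the study intervention and will be analyzed according to the initial randomization assignment". The arm comparisons in 9.4.5, which cover solicited events, related events and serious events for each dose arm against control, follow in the same section with no other population named.

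For a subject whose regimen differs from assignment, 9.4.5 adds that "a per-protocol analysis will be performed as a secondary analysis, which will include subjects according to the product they actually receive in the study".

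Section 9.3 already uses the term per-protocol for something else: randomized subjects who "receive the study intervention consistent with the initial randomization assignment and complete the scheduled visits", analysed by assignment. The next sentence of 9.3 provides, in addition, an as-treated analysis by actual intervention for subjects who received something other than their assignment.

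Section 8.4.3.2 sets the inclusion rule: "All subjects exposed to study agents MUST be included in the safety dataset".

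**The concern.** Safety tables are normally read as a statement about what subjects were exposed to. Under 9.4.5 with 9.3, a placebo-assigned subject who was infused with CIS43LS would have a reaction tabulated under placebo. A subject given the other dose level would have it tabulated under the wrong dose. Both errors blur the contrast that the safety comparison is meant to show, and with rare events a single misplaced case can reverse the direction of a row.

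The secondary analysis is where a reader would look for the correction. Its name points to a set that, by its 9.3 definition, cannot contain the mis-dosed subject, while its description in 9.4.5 requires that subject to be included under the product received. A programmer cannot follow both sections. One who follows the label would produce a table without the subjects who triggered it.

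**Working it through.** **The plan's own safety figure.** Table 5 (section 9.2.2) is the only numerical plan for the adverse-event comparison. For 110 per arm, a placebo rate of 1.0% and two-sided alpha 0.025, it gives detectable CIS43LS rates of 10.7% (80% power) and 13% (90% power). With the pooled-variance normal approximation,

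power = Φ{ [ |p1 − p0| − z·√(2·p̄(1−p̄)/n) ] / √( [p0(1−p0) + p1(1−p1)]/n ) }, where z = 2.241 and p̄ = (p0 + p1)/2.

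For p0 = 0.010, p1 = 0.107 and n = 110: p̄ = 0.0585, the pooled term is 2.241 × 0.0316 = 0.0709, and the denominator is 0.0310. So (0.0970 − 0.0709)/0.0310 ≈ 0.84 and power is 0.800. For p1 = 0.130 power is 0.900. Table 5 reproduces and is not in dispute; it assumes that each arm received its assigned product.

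**The two sections side by side**

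| Question | MITT (9.3), primary for safety | Per-protocol (9.3) | Per-protocol as described in 9.4.5 | As-treated (9.3) |
|---|---|---|---|---|
| Mis-dosed subject included? | Yes | No | Yes | Yes |
| Grouped by | Assignment | Assignment | Product received | Product received |
| Scheduled visits must be completed? | No | Yes | Not stated | Not stated |

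The third and fourth columns of definitions agree on inclusion and grouping. The second and third share a name and contradict each other. The first column is the one that feeds the primary tables.

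**Size for one subject.** Take 110 per arm (section 4.1), and suppose that one placebo-assigned subject receives CIS43LS at one dose level and has the only related serious event.

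- By assignment: placebo 1/110 = 0.9%, CIS43LS arm 0/110 = 0%.
- As treated: placebo (1 − 1)/(110 − 1) = 0/109 = 0%, CIS43LS (0 + 1)/(110 + 1) = 1/111 = 0.9%.

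One subject moves an arm's rate by about 1/110 = 0.9 points, and in this case the direction of the difference reverses. The denominators move with the subject.

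**Size for several subjects (assumed illustration).** The documents give no count of mis-dosed subjects. Assume that k placebo-assigned subjects receive CIS43LS, that all k have the event, that 10 exposed subjects have it in total, and that nobody truly on placebo does. Two-sided Fisher exact tests, CIS43LS against placebo:

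| k | By assignment | p | As treated | p |
|---|---|---|---|---|
| 1 | 9/110 vs 1/110 | 0.019 | 10/111 vs 0/109 | 0.0016 |
| 2 | 8/110 vs 2/110 | 0.10 | 10/112 vs 0/108 | 0.0016 |
| 3 | 7/110 vs 3/110 | 0.33 | 10/113 vs 0/107 | 0.0016 |

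This is close to a worst case, because every mis-dosed subject is assumed to have the event. It shows the direction of the bias and is not a forecast.

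**The case against.** The strongest defence is that the intent of 9.4.5 is clear. The secondary analysis is triggered by mis-dosed subjects and described as grouping by product received, so it cannot sensibly leave them out; the specific description should govern over a borrowed label. Section 9.3 separately commits to an as-treated analysis for the same cases. This stands. A reader might infer that no planned analysis corrects attribution, and the documents do not support that.

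Two further inferences are tempting and also fail.

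- *That non-completers would disappear from safety, up to 10% of 110 = 11 per arm.* The 10% is a drop-out assumption for efficacy power in 9.2.2. Section 9.4.5 sets no visit-completion condition, and the primary MITT set keeps every dosed randomized subject. A narrower secondary table would not in itself breach 8.4.3.2.
- *That the 18 open-label dose-escalation subjects are left out because MITT refers to randomized subjects.* Section 9.3.1 makes all subjects evaluable for toxicity from first treatment, 8.4.3.2 covers everyone exposed, and 9.4.2 sends the primary safety endpoint, which belongs to the dose-escalation study, to 9.4.5. That section summarizes events by dose arm before turning to the efficacy study.

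It is also fair to say that a single serious event would not be hidden. Section 9.4.5 plans individual line listings with severity and relationship to product, serious events are reported individually (8.4.2.3.2, 8.4.4.3), and 8.4.1 lists significant administration errors among the examples of unanticipated problems.

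None of this changes the primary rule. The headline safety tables and arm comparisons still group by assignment, and the naming conflict remains.

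**Conclusion.** The point holds in limited form. The primary safety analysis attributes a mis-dosed subject's events to the arm assigned, in both the tables and the dose-versus-control comparisons. The planned correction is only secondary, and its name in 9.4.5 contradicts 9.3.

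The effect depends on mis-dosing, which the plan expects to be rare and does not quantify. It is about 0.9 points per subject in a 110-subject arm: negligible for common events, but able to reverse a row for a single related or serious event. If nobody is mis-dosed, it is zero. Efficacy estimates, power and type I error are untouched. The change is worth making because the stated rule gives the wrong attribution whenever it matters and the remedy is conventional and cheap.

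**What to change.** In section 9.4.5:

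1. Define the primary safety set as all subjects who received any study agent, in both study parts, grouped by product and dose level actually received. Naming both parts is only a clarification.
2. Use that set for the primary safety tables and for the efficacy-study comparisons of each dose arm with placebo. Keep the table by assigned arm as secondary.
3. Replace the term per-protocol with as-treated, so that the name agrees with 9.3 and the set with 8.4.3.2. State that the 9.3 per-protocol set is not used for safety.

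The cost is a wording change to the protocol's statistical section, with the ethics review that any amendment needs. No data collection, sample size or efficacy analysis changes. If nobody is mis-dosed, the efficacy-study safety tables are identical under either rule.
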